6.7 Subjects stopped / withdrew from the trial

The guardian of the subject has the right to withdraw the infant from the trial at any time. In addition, the investigator may discontinue the subject at any time if the investigator considers it necessary for reasons including:

• Ineligible (ignored during screening, occurred during the study or found by review);

- Serious protocol deviation occurs;
- Serious non to protocol or test requirements;
- Termination of the designated formula or failure to follow the trial procedures due to an adverse event;

• Need to discontinue the designated formula or cause the inability to follow the trial procedures due to disease progression;

- Withdraw informed consent or remove informed consent;
- Misvisit.

If a subject withdraws from the trial due to an adverse event, the investigator will schedule a follow-up visit or telephone visit until the adverse event is resolved or is stable. Data collected before withdrawal will be used for analysis. If a subject withdraws from the trial, the subject will not be replaced. The reason for the withdrawal will be documented in the case report form.

7 Research products

7.1 burden

(1) Ingredients list of test milk powder

The test milk powder was produced by Feihe (Jilin) Dairy Co., LTD. Three formulations were used for infants aged 0-3 months, 3-6 months and 6-12 months respectively. All products are produced in strict accordance with Good Production Practice (GMP), and all indicators meet the requirements of relevant standards and regulations. Compared with the control milk powder, 2 ' -fucinose based lactose, lactose-N-new tetrosaccharide, bifidobacterium longum BB536 are the added ingredients unique to the test milk powder, and the ingredients are as follows:

0 to 3 months old infants: raw milk, lactose, edible plant blend oil (1,3-linoleic acid 2-palmitate triglyceride, sunflower oil, coconut oil, flaxseed oil), desalting whey powder, oligo galactose, whey protein powder, whey protein powder, 2'-fucoose based lactose, lactose-N-new four sugar, phospholipids, vitamin A, vitamin D, vitamin E, vitamin K, vitamin B₁, vitamin B₂, vitamin B₆, vitamin B₁₂, Niacin, folic acid, pantothenate, vitamin C, biotin, choline, sodium citrate, potassium chloride, copper sulfate, magnesium sulfate, iron pyrophosphate, zinc sulfate, magnese sulfate, calcium carbonate, calcium hydrogen phosphate, potassium iodate, sodium selenite, innositol, taurine, docosahexaenoic acid (DHA), arachidonic acid (ARA), lutein, nucleotide, disodium disdium 5'-monophosphate, 5 ', disodium), Bb-12, Bifidobacterium longum B B536.

3-6 months old infants: raw milk, lactose, edible plant blend oil (1,3-linoleic acid 2-palmitate triglyceride, sunflower oil, coconut oil, flaxseed oil), oligo galactose, whey protein powder, desalting whey powder, whey protein powder, 2'-fucoidan based lactose, lactose-N-new four sugar, phospholipids, vitamin A, vitamin D, vitamin E, vitamin K, vitamin B₁, vitamin B₂, vitamin B₆, vitamin B₁₂, Niacin, folic acid, pantothenic acid, vitamin C, biotin, biotin, choline, sodium citrate, potassium chloride, copper sulfate, magnesium sulfate, iron pyrophosphate, zinc sulfate, manganese sulfate, calcium carbonate, calcium hydrogen phosphate, potassium iodiite, sodium selenite, inositol, hexanotide (DHA), arachidonic acid (ARA), lutein, nucleotide, disodium, 5 ' -monomonophosphate, disodium), lactoferrin, Bb-12, Bifidobacterium longum B B536.

6-12 months old infants: raw milk, lactose, edible plant blend oil (1,3-linoleic acid 2-palmitate triglyceride, sunflower oil, coconut oil, flaxseed oil), oligo galactose, whey protein powder, milk powder, whey protein powder, 2'-fucose lactose, lactose-N-new tetrosaccharide, phospholipids, vitamin A, vitamin D, vitamin E, vitamin K, vitamin B₁, vitamin B₂, vitamin B₆, vitamin B₁₂, Niacin, folic acid, pantothenic acid, vitamin C, biotin, biotin, choline, sodium citrate, potassium chloride, copper sulfate, magnesium sulfate, iron pyrophosphate, zinc sulfate, magnese sulfate, calcium carbonate, calcium hydrogen phosphate, potassium iodiite, sodium selenite, inositol, hexanotide (DHA), arachidonic acid (ARA), lutein, nucleotide, disodium, 5 ' - monomonophosphate, disodium), lactoferrin, Bb-12, Bifidobacterium longum B B536.

(2) Control with the ingredients list of milk powder

The control milk powder is commercially available infant formula, with a total of two formulas, which are suitable for infants aged 0-6 months and 6-12 months respectively. All the indicators of the products meet the requirements of the relevant standards and regulations. The list of ingredients is as follows:

0 to 6 months old baby: raw milk, desalting whey powder, edible plant blend oil (1,3-linoleic acid 2-palmitate triglyceride, sunflower oil, coconut oil, linseed oil), lactose, oligo galactose, walnut oil, whey protein powder, whey protein powder, vitamin A, vitamin D, vitamin E, vitamin K, vitamin B₁, vitamin B₂, vitamin B₆, vitamin B₁₂, Niacin, folic acid, pantothenate, vitamin C, biotin, choline, sodium citrate, potassium chloride, copper sulfate, magnesium sulfate, iron pyrophosphate, zinc sulfate, magnese sulfate, calcium carbonate, calcium hydrogen phosphate, potassium iodate, sodium selenite, innositol, taurine, levosnitine, dococarpohexenoic acid (DHA), arachidonic acid (ARA), lutein, lutein, nucleotide (5 ' -cytitilate, 5 ' , 5 ' monophosphate, 5 ' , 5 ' -inolate), bifidobacterium Bb-12.

6-12 months of older infants: raw milk, lactose, desalting whey powder, edible plant blend oil (1,3-linoleic acid 2-palmitate glyceride, sunflower oil, coconut oil, linseed oil), milk powder, oligomic galactose, whey protein powder, whey protein powder, walnut oil, vitamin A, vitamin D, vitamin E, vitamin K, vitamin B₁, vitamin B₂, vitamin B₆, vitamin B₁₂, Niacin, folic acid, pantothenate, vitamin C, biotin, choline, sodium citrate, potassium chloride, copper sulfate, magnesium sulfate, iron pyrophosphate, zinc sulfate, manganese sulfate, calcium carbonate, calcium hydrogen phosphate, potassium iodate, sodium selenite, innositol, taurine, levosnitine, dococarpohexenoic acid (DHA), arachidonic acid (ARA), lutein, lutein, nucleotide (5 ' -cytitilate, 5 ' , 5 ' monophosphate, 5 ' , 5 ' -inolate), bifidobacterium Bb-12.

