3.4 Bifidobacterium long long subspecies BB536

Bifidobacterium BB536 isolated the intestines of healthy infants in 1969 and has been approved for infant food in Japan and the United States. It is the first affinity human Bifidobacterium strain (HRB) recognized by the US FDA. At the same time, in 2022, it was approved to be included in China's list of edible fungus list.

As of March 2022, more than 220 academic papers were published based on BB536. A number of clinical studies on infants at home and abroad have proved that the strain has good food safety. Studies have proved that BB536 is effective in maintaining intestinal health, improving immunity, and preventing infection.

3 Study purpose and significance

To compare the effects of breast milk oligosaccharide and multinutrientoptimized infant formula and conventional infant formula on the intestinal health of infants under 1 year of age. In comparison with breast-fed infants, the effects of different infant formulas on infant growth and development, cognitive development, immune function, intestinal comfort, crying, and upper respiratory tract infection were explored.

4 research contents

This trial is a multicenter, randomized, controlled, parallel, double-blind, exploratory trial to compare the effects of infant formula, conventional infant formula on infant formula and breast milk in early life.

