6.5.1 Random group table

Randtrial block randomization. The randomization tables were generated simulated on a computer by an unblinded statistician using the SAS software according to the random number table. Trial or control milk powder were coded according to the randomization table. Each center will compete for entry. In clinical operation, the authorized investigator or the research assistant will distribute the test or control milk powder according to Powder No. Any deviations should be truthfully recorded for evaluation before data analysis.

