6.6 Interview

6.6.1 Visit 1

Visit 1 will be performed on the 28th day of life and the investigator will obtain the following information:

· Mode of delivery;

· Pregnancy-related complications;

· Parents' physical condition (height, weight, medical history);

· Parents' living habits (smoking history, drinking history, exercise habits);

· Parents' social and economic background (education level, employment status);

· Growth and development parameters (height, head circumference, chest circumference, body weight);

- Stool samples (16S rRNA, SCFAs, sIgA);
- · Gastrointestinal comfort survey and questionnaire;
- · Questionnaire on baby crying condition;
- · Questionnaire on infant diarrhea;
- · Questionnaire on upper respiratory tract infection in infants;

⁵⁷Steenhout P, Sperisen P, Martin F, et al.Term Infant Formula Supplemented with Human Milk Oligosaccharides (2' Fucosyllactose and Lacto - N - neotetraose) Shifts Stool Microbiota and Metabolic Signatures Closer to that of Breastfed Infants[J].The FASEB Journal, 2016, 30.

- · The Bristol Stool Classification Questionnaire;
- · Past medical history and current medical history.

6.6.2 Visit 2

Visit 2 will be conducted on Birth Day 90 with a window of 3 days and the investigator will measure and obtain the following information:

· Growth and development parameters (height, head circumference, chest circumference, body weight);

- · Gastrointestinal comfort survey and questionnaire;
- · Questionnaire on baby crying condition;
- · Questionnaire on infant diarrhea;
- · Questionnaire on upper respiratory tract infection in infants;
- · The Bristol Stool Classification Questionnaire;
- · Adverse events and serious adverse events.

6.6.3 Visit 3

Visit 3 will be conducted on Post Birth Day 180 with a window of 5 days and the investigator will measure and obtain the following information:

· Growth and development parameters (height, head circumference, chest circumference, body weight);

- Blood samples (hsCRP, analysis of lymphocyte subsets, amino acids, osteocalcin, alkaline phosphatase, albumin);
- Stool samples (16S rRNA, SCFAs, sIgA);
- · Gastrointestinal comfort survey and questionnaire;
- · Questionnaire on baby crying condition;
- · Questionnaire on infant diarrhea;
- · Questionnaire on upper respiratory tract infection in infants;
- · The Bristol Stool Classification Questionnaire;
- · Adverse events and serious adverse events.

6.6.4 Visit 4

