7.3 Sample management

All trial milk powder for the study will be provided to the subjects free of charge. The trial and control powder were stored in the central warehouse and distributed by the investigator by subject number and trial protocol.

8 Outcome indicators

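### Called double-blind, but only test infants have a scheduled product change at about 3 months, and the masking described gives control infants no matching changeover

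*Protocol*

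**What the plan says.** The summary and Section 4 both label the trial double-blind; Section 4 reads "This trial is a multicenter, randomized, controlled, parallel, double-blind, exploratory trial".

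Section 7.1 then sets the product stages. Test powder: "Three formulations were used for infants aged 0-3 months, 3-6 months and 6-12 months respectively". The control is a commercially available formula "with a total of two formulas, which are suitable for infants aged 0-6 months and 6-12 months respectively". Section 7.2 follows the same pattern: the 3-6 month test product has its own composition table, while a single table covers the control from 0 to 6 months.

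On masking, Section 6.5.1 has the list generated "by an unblinded statistician using the SAS software" and adds that "Trial or control milk powder were coded according to the randomization table". At the sites, "the authorized investigator or the research assistant will distribute the test or control milk powder according to Powder No". Section 7.3 says that powder is kept in a central warehouse and "distributed by the investigator by subject number and trial protocol".

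On outcomes, Section 6.6 assigns data collection to the investigator. Visit 2, for example, is held "with a window of 3 days and the investigator will measure and obtain the following information".

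**The concern.** Coding a powder hides its name. It does not by itself hide that one arm moves to a new stage at an age when the other arm does not. If the stage change can be seen in the supply, an infant who changes at 3 months is on test and an infant who does not is on control, so both arms become inferable. Both schedules are printed in the protocol that site staff work from, and no section separates the person who hands out powder from the person who obtains outcomes.

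Outcomes that involve judgement or reporting are at stake after that age: adverse events, and the comfort, crying, diarrhoea, respiratory and stool questionnaires. A difference between the formula arms in these could partly reflect knowledge of the arm. The concern applies only to the two randomised formula arms; the breastfeeding group cannot be blinded in any case.

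**Working it through.** **Product changes, from Section 7.1.**

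| Age | Test | Control |
|---|---|---|
| 0-3 months | stage 1 | stage 1 |
| 3-6 months | stage 2 | stage 1 |
| 6-12 months | stage 3 | stage 2 |

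Changes equal stages minus one. Test: 3 − 1 = 2, at 3 and 6 months. Control: 2 − 1 = 1, at 6 months. The difference is one change, at 3 months, in the test arm only. Infants enter at 0-28 days of age, so every test infant still on product at 3 months is scheduled to pass through it.

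**Is it a real change of product?** The first test table in Section 7.2 is taken as the 0-3 month product, because it precedes the 3-6 month table. Protein goes from 12.5 to 9.5 g per 100 g: (12.5 − 9.5) / 12.5 = 24% lower. Carbohydrate goes from 52.3 to 55.3 g per 100 g. The control keeps one composition throughout 0-6 months. These figures show that the product changes, not that anyone handling it would notice. I do not rely on L-carnitine, casein phosphopeptides or lactoferrin, because the ingredient lists in Section 7.1 and the tables in Section 7.2 disagree on them.

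**Timing.** Section 4 gives the intervention period as 332 days, which reproduces: 360 − 28 = 332. Taking 3 months as day 90 to 92 (an assumption):

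- Visit 2 is 90 ± 3, days 87-93, so the change falls inside its window.
- Visit 3 is 180 ± 5, days 175-185. Its earliest date is 175 − 92 = 83 to 175 − 90 = 85 days after the change.
- Visit 4 is 360 ± 7, days 353-367. It has the only Bayley assessment.
- Time from the change to day 360 is 360 − 92 = 268 to 360 − 90 = 270 days, and 268/332 and 270/332 are both about 81%.

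Elapsed time is the fairer measure for adverse events, because Section 10.2 requires all events during the study to be reported, not only those found at visits.

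**Does the described masking cover the change?** The steps are coding from the randomisation table (6.5.1), distribution by powder number (6.5.1) and distribution by subject number (7.3). None splits the control's 0-6 month supply, sets a control changeover at 3 months or matches the packs. The number of allocations that could be inferred cannot be calculated from the document.

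**The case against.** The strongest reply is that this argues from silence. The protocol does not say that the stage shows on a pack, or that the powder number changes at 3 months in one arm only. Coding is a masking step, and issuing the control under two codes would be compatible with Section 6.5.1 and may already be intended. Packaging detail may sit in a handling document, and the Section 6.1 flow chart is not shown. This stands as a limit on the finding: a reader might infer that the blind is broken, and the text does not support that. It does not remove the point, because the schedules as written are unequal and the masking as written does not address it.

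Other stronger readings also fail:

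- *The Bayley assessment is the most exposed outcome.* Nothing shows that the examiner handles powder or knows the supply history, and by day 360 both arms have been on their 6-12 month product for about six months. Exposure is possible only.
- *Whoever conducts Visit 2 sees the change.* Visit 2 lists no dispensing.
- *Adverse-event results turn on the relatedness judgement.* Section 10.2 records it, but Section 9.6 plans no summary by relatedness. Some exposure remains, since Section 4 refers to relatedness in defining an adverse event.
- *Sections 6.5.1 and 7.3 contradict each other on who dispenses.* They are largely compatible; one is more detailed.
- *Site staff are not meant to be blinded.* Naming one unblinded statistician in a trial labelled double-blind suggests the opposite.

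The trial is exploratory, and Section 9.2 puts description ahead of inference. That limits the consequence, but a descriptive comparison is no better protected against reporting bias.

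**Conclusion.** The point holds as a risk to the blind and should be fixed. One scheduled product change, at about 3 months, belongs to the test arm alone, and the masking described does not cover it. Because the investigator distributes powder under Section 7.3 and obtains outcomes under Section 6.6, staff who handle supplies and know Section 7.1 could infer the arm for roughly the last 81% of the intervention period.

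The risk falls mainly on adverse events and the tolerance questionnaires, whether investigator- or guardian-reported. For the questionnaires it is less certain, since the protocol does not say that guardians know either schedule. It reaches the Bayley assessment only if the examiner knows the supply history. A reader might infer that the primary endpoint is compromised; 16S rRNA and SCFAs are laboratory measures, affected at most indirectly through feeding or withdrawal decisions.

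The conclusion assumes that Section 7.1 is followed as written and that the 3-month stage change can be recognised from the supply. The second assumption cannot be confirmed or excluded from the readable text.

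**What to change.** Leave both products unchanged. Issue the control 0-6 month powder under two stage codes, 0-3 and 3-6 months, in packs matched to the test packs, so that code changes fall at the same ages in both arms. State this in Sections 6.5.1 and 7.3. If an equivalent arrangement already exists, one sentence describing it in those sections is enough.

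If packs have already been released without it, state who is actually blinded, and report the subjective outcomes after 3 months as open to possible unblinding.

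The cost is relabelling or over-packing the control powder, a longer code list and some extra dispensing work. Visits and sample size do not change. If packs are already out, the change is to text only.

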7.2 Nutritional composition table

(1) Nutrition composition list of test milk powder

project	unit	Every 100 kJ	Every 100g
energy	kJ	100	2097
protein	g	0.60	12.5
fat	g	1.24	26.0
linoleic acid	g	0.20	4.1
α-linolenic acid	mg	20	410
carbohydrate	g	2.5	52.3
vitamin			
vitamin A	μg RE	17	360
vitamin D	μg	0.62	13.0
vitamin E	mg α-TE	0.29	6.00
vitamin K1	μg	2.86	60.0
vitamin B ₁	μg	31	650
vitamin B ₂	μg	24	500
vitamin B ₆	μg	19.1	400
vitamin B ₁₂	μg	0.072	1.50
niacin	μg	196	4100
folic acid	μg	4.3	90
pantothenic acid	μg	145	3050
vitamin C	mg	3.3	70.0
biotin	μg	0.76	16.0
bilineurine	mg	10.3	215.0
mineral substance			
sodium	mg	8	175
potassium	mg	18	385
copper	μg	16.7	350
magnesium	mg	1.5	32
iron	mg	0.24	5.0

zinc	mg	0.21	4.50
manganese	μg	1.91	40
calcium	mg	17	350
phosphorus	mg	10	220
iodine	μg	5.1	106.0
chlorine	mg	13	280
Se	μg	0.91	19.0
Available ingredients			
inose	mg	1.9	40.0
taurine	mg	1.8	38.0
Docosahexaenoic acid (DHA)	mg	4.6	97.0
Eicosapentetraenoic acid (ARA)	mg	7.9	164.9
The oligomeric galactose	g	0.14	3.0
2 ' -fucoose-based lactose	g	0.037	0.78
Lactose-N- neotetrasaccharide	g	0.019	0.39
1,3-dioleic acid 2- palmitate triglyceride	g	0.36	7.5
lutein	μg	3.8	80
ribotide	mg	1.4	30.0
lactoferrin	mg	23.8	500.0

Table 2 Nutrient composition list of 3-6 month old test samples

project	unit	Every 100 kJ	Every 100g
energy	kJ	100	2097
protein	g	0.45	9.5
fat	g	1.24	26.0
linoleic acid	g	0.20	4.1
α-linolenic acid	mg	20	410
carbohydrate	g	2.6	55.3
vitamin			
vitamin A	μg RE	17	360
vitamin D	μg	0.62	13.0
vitamin E	mg α-TE	0.29	6.00
vitamin K ₁	μg	2.86	60.0
vitamin B ₁	μg	31	650
vitamin B ₂	μg	24	500
vitamin B ₆	μg	19.1	400
vitamin B ₁₂	μg	0.072	1.50
niacin	μg	196	4100
folic acid	μg	4.3	90
pantothenic acid	μg	145	3050

vitamin C	mg	3.3	70.0
biotin	μg	0.76	16.0
bilineurine	mg	10.3	215.0
mineral substance			
sodium	mg	8	175
potassium	mg	18	385
copper	μg	16.7	350
magnesium	mg	1.5	32
iron	mg	0.24	5.0
zinc	mg	0.21	4.50
manganese	μg	1.91	40
calcium	mg	17	350
phosphorus	mg	10	220
iodine	μg	5.1	106.0
chlorine	mg	13	280
Se	μg	0.91	19.0
Available ingredients			
inose	mg	1.9	40.0
taurine	mg	1.8	38.0
L-carnitine	mg	0.4	9.0
Docosahexaenoic acid (DHA)	mg	4.6	97.0
Eicosapentetraenoic acid (ARA)	mg	7.9	164.9
The oligomeric galactose	g	0.14	3.0
2 ' -fucoose-based lactose	g	0.037	0.78
Lactose-N- neotetrasaccharide	g	0.019	0.39
1,3-dioleic acid 2- palmitate triglyceride	g	0.36	7.5
lutein	μg	3.8	80
ribotide	mg	1.4	30.0
lactoferrin	mg	23.8	500.0
Casein phosphopeptides	mg	6.2	130.0
	1	I	1

project	unit	Every 100kJ	Every 100g
energy	kJ	100	2012
protein	g	0.57	11.5
fat	g	1.07	21.5
linoleic acid	g	0.14	2.8
α-linolenic acid	mg	14	280
carbohydrate	g	2.9	58.3

vitamin			
vitamin A	μg RE	22	450
vitamin D	μg	0.60	12.0
vitamin E	mg α-TE	0.24	4.90
vitamin K1	μg	2.24	45.0
vitamin B ₁	μg	30	600
vitamin B ₂	μg	38	760
vitamin B ₆	μg	14.9	300
vitamin B ₁₂	μg	0.060	1.20
niacin	μg	194	3900
folic acid	μg	3.0	60
pantothenic acid	μg	204	4100
vitamin C	mg	3.3	66.0
biotin	μg	0.60	12.0
bilineurine	mg	9.9	200.0
mineral substance			
sodium	mg	7	135
potassium	mg	21	420
copper	μg	11.9	240
magnesium	mg	1.6	33
iron	mg	0.30	6.0
zinc	mg	0.20	4.00
manganese	μg	1.89	38
calcium	mg	22	450
phosphorus	mg	13	270
iodine	μg	4.5	90.0
chlorine	mg	14	280
Se	μg	0.60	12.0
Available ingredients			
inose	mg	2.0	40.0
taurine	mg	1.9	38.0
L-carnitine	mg	0.5	10.0
Docosahexaenoic acid (DHA)	mg	4.7	95.0
Eicosapentetraenoic acid (ARA)	mg	8.0	161.5
The oligomeric galactose	g	0.15	3.0
2 ' -fucoose-based lactose	g	0.024	0.48
Lactose-N- neotetrasaccharide	g	0.010	0.21
1,3-dioleic acid 2- palmitate triglyceride	g	0.25	5.0

lutein	μg	10.4	210
ribotide	mg	1.5	30.0
lactoferrin	mg	24.9	500.0
Casein phosphopeptides	mg	8.3	167.0

(2) Nutrient composition table of the control samples

Table Nutrient composition list of control samples from 4 0 to 6 months of age

project	unit	Every 100kJ	Every 100g
energy protein	kJ	100	2173
	g	0.48	10.5
fat	g	1.25	27.2
linoleic acid	g	0.17	3.8
α-linolenic acid	mg	19	423
carbohydrate	g	2.6	57.3
vitamin			
vitamin A	μg RE	17	360
vitamin D	μg	0.60	13.0
vitamin E	mg α-TE	0.28	6.00
vitamin K ₁	μg	2.58	56.0
vitamin B ₁	μg	29	623
vitamin B ₂	μg	28	600
vitamin B ₆	μg	18.4	400
vitamin B ₁₂	μg	0.069	1.50
niacin	μg	189	4100
folic acid	μg	3.3	72
pantothenic acid	μg	138	3000
vitamin C	mg	3.3	72.0
biotin	μg	0.74	16.0
bilineurine	mg	9.9	215.0
mineral substance			
sodium	mg	8	175
potassium	mg	18	400
copper	μg	16.6	360
magnesium	mg	1.4	31
iron	mg	0.21	4.5
zinc	mg	0.18	4.00
manganese	μg	1.98	43
calcium	mg	17	360
phosphorus	mg	10	210

iodine	μg	4.9	106.0
chlorine	mg	14	297
Se	μg	0.87	19.0
Available ingredients			
inose	mg	1.8	40.0
taurine	mg	1.7	38.0
L-carnitine	mg	0.4	9.0
Docosahexaenoic acid (DHA)	mg	4.5	97.0
Eicosapentetraenoic acid (ARA)	mg	7.6	164.9
The oligomeric galactose	g	0.08	1.7
1,3-dioleic acid 2- palmitate triglyceride	g	0.27	5.8
lutein	μg	3.0	66
ribotide	mg	1.4	30.0

Table 5 Nutrient composition list of control samples from 6-to 12 month old

project	unit	Every 100 kJ	Every 100g
energy	kJ	100	2058 11.5
protein	g	0.56	
fat	g	1.07	22.0
linoleic acid	g	0.14	2.8
α -linolenic acid	mg	14	280
carbohydrate	g	3.0	61.0
vitamin			
vitamin A	μg RE	22	450
vitamin D	μg	0.58	12.0
vitamin E	mg α-TE	0.22	4.50
vitamin K ₁	μg	1.75	36.0
vitamin B ₁	μg	30	610
vitamin B ₂	μg	34	700
vitamin B ₆	μg	14.6	300
vitamin B ₁₂	μg	0.058	1.20
niacin	μg	190	3900
folic acid	μg	2.9	60
pantothenic acid	μg	155	3200
vitamin C	mg	3.3	67.0
biotin	μg	0.78	16.0
bilineurine	mg	9.7	200.0

sodium	mg	7	135
potassium	mg	21	430
copper	μg	11.7	240
magnesium	mg	1.6	33
iron	mg	0.29	6.0
zinc	mg	0.19	4.00
manganese	μg	1.85	38
calcium	mg	22	450
phosphorus	mg	13	270
iodine	μg	4.4	90.0
chlorine	mg	12	250
Se	μg	0.58	12.0
Available ingredients			
inose	mg	1.2	25.0
taurine	mg	1.8	38.0
L-carnitine	mg	0.4	9.0
Docosahexaenoic acid (DHA)	mg	4.6	95.0
Eicosapentetraenoic acid (ARA)	mg	7.8	161.5
The oligomeric galactose	g	0.07	1.4
1,3-dioleic acid 2- palmitate triglyceride	g	0.18	3.8
lutein	μg	10.2	210
ribotide	mg	1.5	30.0

